4.11.2 Clinical Laboratory Evaluation

All safety laboratory analyses will be performed by local laboratories, the respective reference ranges will be used by the investigator to assess abnormality, which will be captured in the CRF as an overall assessment:

- Normal
- Abnormal – Clinically Significant
- Abnormal – Not Clinically Significant

with specification of the laboratory assessment in case of clinically significant abnormality.

Laboratory values will not be received for analysis.

The assessments will be listed in parameter groups:

- Urinalysis
- Viral Serology
- Hematology
- Chemistry

and are scheduled to be collected for:

- Visit 1
- Visit 2 (only drug test)
- Visit 3, Day 1 (pre-dose)
- Visit 3, Day 8 (only drug test)
- Visit 4
- Visit 5

The overall assessment and each specified clinically significant abnormal parameter will be listed for each patient and visit/timepoint by treatment group including age, sex and any additional details recorded on the eCRF for abnormal clinically significant.

CONFIDENTIAL

Project Document Version No. 2.0

Effective Date: 30 Jan 19

Project Document Effective Date: Date of last signature

Related to: [REDACTED]

Page 38 of 41

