1.4.2 Risks

Procedure-related risks

The use of an indwelling venous catheter or venepuncture for e.g. blood sampling may result in mild bruising and, in rare cases, in transient inflammation of the wall of the vein, or nerve injury, potentially resulting in paraesthesia, reduced sensibility, and/or pain for an indefinite period.

The total volume of blood withdrawn per patient during the entire study will not exceed 300 mL. This is less than the volume of a normal blood donation (500 mL). No health-related risk to patients is expected from withdrawal of this volume of blood.

Drug-related risks and safety measures

Participants will be closely monitored during the trial participation (including safety laboratory, AE monitoring, physical and neurological examinations) to ensure that worsening of pre-existing conditions or any newly occurring events are detected and any necessary actions taken according to stopping criteria (see section [3.3.4](#)).

Suicide related behaviour (suicide attempts and suicidal ideation) has been reported in patients treated with atomoxetine.

Risk mitigation:

In the interest of ensuring participant safety, trial participants will be proactively screened and monitored for SIB.

Atomoxetine can affect heart rate and blood pressure. Most patients taking atomoxetine experience a modest increase in heart rate (mean <10 bpm) and/or increase in blood pressure (mean <5 mm Hg).

Risk mitigation:

- Subjects with relevant findings in BP, PR or ECG at Screening, cardiovascular disorders, history of relevant hypertension or orthostatic hypotension, fainting spells or blackouts, use of drugs that might prolong the QT/QTc interval, marked (Section [3.3.3](#)), or subjects with additional risk factors for Torsade de Pointes arrhythmia (Section [3.3.3](#)) are excluded from trial participation.
- Heart rate and blood pressure be measured and recorded before treatment is started and, during treatment, after dose adjustment to detect possible clinically important increases.

Very rarely, spontaneous reports of liver injury, manifested by elevated hepatic enzymes and bilirubin with jaundice, have been reported.

Risk mitigation:

- Liver enzymes (ALT, AST) will be measured before, during and after dosing.
- Atomoxetine will be discontinued in patients with jaundice or laboratory evidence of liver injury.

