7.2.6 Safety analyses

Adverse events will be coded using the Medical Dictionary for Drug Regulatory Activities (MedDRA). Standard BI summary tables and listings will be produced. All adverse events with an onset between start of treatment and end of the REP, a period of 4 days the last dose of trial medication, will be assigned to the on-treatment period for evaluation.

All treated patients will be included in the safety analysis. In general, safety analyses will be descriptive in nature and will be based on BI standards. No hypothesis testing is planned.

Statistical analysis and reporting of adverse events will concentrate on treatment-emergent adverse events, i.e. all adverse events occurring between start of treatment and end of the REP. Adverse events that start before first drug intake and deteriorate under treatment will also be considered as 'treatment-emergent'.

Frequency, severity, and causal relationship of adverse events will be tabulated by system organ class and preferred term after coding according to the current version of the Medical Dictionary for Drug Regulatory Activities (MedDRA) at database lock.

Laboratory data will be analysed both quantitatively as well as qualitatively. The latter will be done via comparison of laboratory data to their reference ranges. Values outside the reference range as well as values defined as clinically relevant will be summarised. Treatment groups will be compared descriptively with regard to distribution parameters as well as with regard to frequency and percentage of patients with abnormal values or clinically relevant abnormal values.

Vital signs, physical examinations, or other safety-relevant data observed at screening, baseline, during the course of the trial and at the end-of-trial evaluation will be assessed with regard to possible changes compared to findings before start of treatment.

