1 INTRODUCTION

This is a study to test different ways to measure the effect of atomoxetine on impulsive behavior in young adults with Attention Deficit Hyperactivity Disorder (ADHD).

There is considerable evidence that disorders clinically associated with impulsivity show impairment on a variety of questionnaire and behavioral measures of impulsivity. The key questions that will be addressed in this study include: (1) Do ADHD patients, with impulsivity as a core characteristic of the disorder, have a distinct behavioral profile based on questionnaire and behavioral laboratory measures before and after treatment with atomoxetine? (2) Are there specific measures that are reliable and sensitive measures of impulsivity which might be used across diagnoses? The answers to these questions are of importance in the selection of outcome measures for treatment and Phase I/II assessments of potential pharmacotherapies for different disorders.

The analyses described in this Statistical Analysis Plan (SAP) are based upon the following study documents:

- Trial Protocol, Version 3.0 (March 16, 2022)
- electronic Case Report Form (eCRF), Version 2.0 (March 09, 2022)

The study will be analyzed as described in the above-mentioned version of the trial protocol unless explicitly specified otherwise.

The content of this SAP is compatible with the International Council for Harmonisation E9 Guidance documents.

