4.13 Changes and Clarifications in the Conduct of the Study or Planned Analysis

Clarification

According to CTP Section 7.2.1, the TS14 analysis set is defined as “The TS14 includes all subjects who were treated according to protocol for at least 90% (not more than one missed dose) of the planned doses of study drug (i.e. placebo or atomoxetine).”, while Section 4.3 defines

CONFIDENTIAL

Project Document Version No. 2.0

Effective Date: 30 Jan 19

Project Document Effective Date: Date of last signature

Related to: [REDACTED]

Page 40 of 41

treatment compliance percentage via number of tablets, the treatment compliance used for analysis of TS14 is according to SAP Section 4.9.2 based of days of study drug intake, not the number of tablets, which is used to monitor study conduct.

Changes

Not applicable.

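### The SAP specifies no by-arm laboratory table, although protocol 7.2.6 plans one and the eCRF categories would still support the frequency part

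*SAP*

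**What the plan says.** Protocol 7.2.6: "Laboratory data will be analysed both quantitatively as well as qualitatively". It goes on to plan a descriptive comparison of the arms on distribution parameters and on the "frequency and percentage of patients with abnormal values or clinically relevant abnormal values".

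SAP 4.11.2: local laboratories analyse the samples, and the investigator records one of three categories in the CRF: normal, abnormal clinically significant, or abnormal not clinically significant. This is done "with specification of the laboratory assessment in case of clinically significant abnormality". Then: "Laboratory values will not be received for analysis". The output is a listing by parameter group: "The overall assessment and each specified clinically significant abnormal parameter will be listed for each patient and visit/timepoint by treatment group". SAP 4.11.3, by contrast, has vital signs both listed and summarised.

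SAP 1 sets the default: "The study will be analyzed as described in the above-mentioned version of the trial protocol unless explicitly specified otherwise". SAP 4.13 contains one clarification, on how compliance is counted for TS14. Under Changes it says "Not applicable".

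Protocol 1.4.2 names liver injury as a rare drug risk, with this mitigation: "Liver enzymes (ALT, AST) will be measured before, during and after dosing".

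**The concern.** Safety is the trial's only secondary objective, and the protocol plans a laboratory comparison between arms as part of it. The SAP drops half of that comparison for lack of data. It does not specify the other half, although the data for it are in the eCRF. The results that lose most are abnormalities judged not clinically significant. They are not adverse events, so the adverse event tables do not count them. In the listing they appear only as an abnormal assessment for a whole parameter group. A modest excess of such results on atomoxetine could be found only by hand-counting a listing. A reader of the report who checks SAP 4.13 would also not learn there that the laboratory analysis differs from the protocol.

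**Working it through.** The plan gives no figure to reproduce, so the check sets the texts side by side.

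**1. Each part of the protocol comparison against the SAP**

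| Planned in protocol 7.2.6, by arm | Data needed | Held under SAP 4.11.2? | Feasible? | Table specified in 4.11.2? |
|---|---|---|---|---|
| Distribution parameters | Numeric values | No | No | No |
| Patients with abnormal values, n and % | Abnormal or not, per patient and visit | Yes, as a category per parameter group | Yes, per group but not per analyte | No |
| Patients with clinically relevant abnormal values, n and % | Clinically significant or not, and which parameter | Yes, both | Yes | No, listing only |

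**2. Does other SAP text restore the table?** SAP 1 keeps the protocol analysis unless the SAP expressly departs from it, and 4.11.2 does not say that the frequency comparison is dropped. SAP 4.2 has general rules: categorical data are given as counts and percentages, repeated variables are summarised at each time point, and tables are generally by arm. These rules set a format and could be read as requiring a table. However, 4.11.2 says only that laboratory assessments are listed, while 4.11.3 says vital signs are listed and summarised. The two readings cannot be reconciled from the text.

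**3. Is the departure recorded?** The absence of values is stated openly in 4.11.2. Section 4.13, where changes from the protocol belong, has no entry for it.

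**4. Where each result ends up**

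- Abnormal, clinically significant: the parameter is named in the listing. It is reported as an adverse event (protocol 5.2.3, SAP 4.11.1) and is tabulated by arm if treatment-emergent.
- Abnormal, not clinically significant: an abnormal category in the listing, with no parameter named and no specified by-arm table.

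**5. How many assessments.** SAP 4.11.2 schedules full safety laboratory tests at Visit 1, Day 1 pre-dose, Visit 4 and Visit 5. Visit 2 and Day 8 are drug tests only. That leaves 2 tests per patient after the first dose.

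- 80 evaluable patients: 80 × 2 = 160 patient-visits. With haematology and chemistry, 160 × 2 = 320 assessments.
- Upper bound, if all 96 patients attend both visits: 96 × 2 = 192 patient-visits, and 192 × 2 = 384 assessments.

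**6. Visit 5 and the treatment-emergent window.** SAP 4.11.1 counts events starting up to 4 days after the last dose, so for a patient dosed to Day 14 the window ends on Day 14 + 4 = Day 18. The protocol flow chart and section 6.2.3 put Visit 5 on Day 19 to 28, which is 19 − 18 = 1 to 28 − 18 = 10 days after the window. Protocol 3.1 and SAP 3.1 put the last visit 4 days after the last intake, which is Day 18 and inside the window. The documents therefore do not settle whether a finding first seen at Visit 5 counts as treatment-emergent.

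**The case against.** The strongest reply has four parts.

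- **The SAP is open about the values.** SAP 4.11.2 says plainly that they are not received, in the section where a reader would look, and SAP 1 allows express departures. This stands for the distribution part. A reader might infer that the departure was concealed, and the text does not support that. What is missing is the matching entry in 4.13.
- **The frequency part may still be in force.** SAP 1 and SAP 4.2 together can be read that way, and the mock shells, which are not available, might contain the table. This stands as far as making the point an ambiguity. It does not remove it, because 4.11.2 specifies a listing and nothing more.
- **Clinically significant findings are covered.** They are named in a listing arranged by arm, and the treatment-emergent ones are tabulated. The Day 14 test comes after 13 of the 14 doses, so findings dated there fall inside the window. A reader might infer that ALT and AST cannot be compared between arms at all, and that is too strong. What is lost is the distribution of values and the parameter-level count of abnormalities judged not clinically significant. The mitigation in protocol 1.4.2 concerns monitoring individual patients and is unaffected. A reader might also infer that every Visit 5 finding misses the treatment-emergent tables. Protocol 3.1 and SAP 3.1 contradict that, and adverse events are in any case collected to the end-of-study visit and listed.
- **The consequence is small.** The safety analysis is descriptive, the drug is approved, treatment lasts 14 days, and the secondary endpoint is the percentage of patients with adverse events. All of this stands and limits the severity.

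**Conclusion.** The mismatch is real and minor. Of the two kinds of by-arm laboratory summary planned in protocol 7.2.6, one is impossible under the SAP and the other is feasible but not specified in SAP 4.11.2. Section 4.13 records neither. About 160 post-dose patient-visits in 80 patients have no specified laboratory table. The practical loss falls on abnormalities judged not clinically significant. The primary endpoints and the treatment-emergent event percentages are not affected. The documents give no abnormality rates, so the size of any imbalance that might go unseen cannot be estimated.

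Three assumptions are made. First, protocol 7.2.6 reads the same in version 3.0, which the SAP cites, as in version 4.0, which was available. The visible amendment entries list no change to it, but the log is not complete. Second, the mock shells do not already contain the table. Third, the eCRF holds the assessment separately for haematology and chemistry, as the SAP's parameter groups suggest.

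**What to change.** 1. In SAP 4.11.2, add one descriptive table by arm and visit (Day 1 pre-dose, Visit 4, Visit 5). For haematology and for chemistry separately, give the number and percentage of TS patients assessed who are normal, abnormal not clinically significant, and abnormal clinically significant. Add the shift from Day 1 pre-dose and a count for each named clinically significant parameter.
2. In SAP 4.13, under Changes, record that the quantitative laboratory analysis in protocol 7.2.6 will not be done because values are not received.

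The cost is a little programming on data already in the eCRF and one short paragraph. No new data are needed, and the adverse event definitions and tables stay as they are. The table has limits: it rests on local reference ranges and investigator judgement, and it pools all chemistry, so it does not isolate ALT or AST. It restores the frequency comparison only at the level of the parameter group.

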4.11.3 Vital Signs, Physical Findings, ECG and Menstrual Cycle Information

The following **vital signs** parameters will be listed and summarized based on the TS.

- Temperature
- Pulse rate (beats/min)
- Systolic blood pressure (mmHg)
- Diastolic blood pressure (mmHg)

will be assessed at

- Visit 1
- Visit 3 (Day 1 pre-dose and 4h post-dose)
- Visit 3 (Day 8)
- Visit 4 (pre-dose and 4h post-dose)
- Visit 5

The overall assessment and each specified clinically significant abnormal parameter will be listed for each patient and visit/timepoint by treatment group including age, sex and any additional details recorded on the eCRF for abnormal clinically significant.

Physical examination will be performed at

- Visit 1
- Visit 3 (Day 1 pre-dose)
- Visit 3 (Day 8)
- Visit 4 (pre-dose)
- Visit 5

Physical exam findings are recorded per the eCRF as weight and height, as well as overall interpretation of body systems:

1. Normal
2. Abnormal – Clinically Significant
3. Abnormal – Not Clinically Significant

and specified only if Abnormal – Clinically Significant.

A by-patient listing of physical exam results will be presented, including the patient identifier, visit, study day of finding, indication of whether exam was performed and reason examination not performed (if applicable), specified body system, physical exam result, additional details recorded on the eCRF for abnormal clinically significant, height and weight.

CONFIDENTIAL

Project Document Version No. 2.0

Effective Date: 30 Jan 19

Project Document Effective Date: Date of last signature

Related to: [REDACTED]

Page 39 of 41

Standard safety **12-lead ECGs** will be performed at

- Visit 1
- Visit 3 (Day 8)
- Visit 4
- Visit 5

The following ECG parameters will be recorded:

- QTc-interval (msec)

The ECG will be evaluated by the Investigator as

- Normal
- Abnormal – Clinically Significant
- Abnormal – Not Clinically Significant

All ECG parameters will be listed by patient and captured time point.

Menstrual cycle information (provision of information and date of last menstrual period) will be captured at each site visit. This information will be presented in a by-patient listing for all female patients.

4.11.4 Safety Monitoring (Independent Data Monitoring Committee, Data Monitoring Committee, Data and Safety Monitoring Board)

Not applicable.

4.12 Determination of Sample Size

No formal testing of hypotheses has been planned for this study. Therefore, no formal sample size calculations were performed.

It is planned to enter a total of 80 evaluable subjects in the trial, because this sample size is considered sufficient to achieve the aims of this exploratory trial with regards to the primary and secondary endpoints, but also concerning the sufficiency of the sample size of further endpoints of particular interest.

For more details, please refer to the Clinical Trial Protocol Section 7.5.

4.13 Changes and Clarifications in the Conduct of the Study or Planned Analysis

Clarification

According to CTP Section 7.2.1, the TS14 analysis set is defined as “The TS14 includes all subjects who were treated according to protocol for at least 90% (not more than one missed dose) of the planned doses of study drug (i.e. placebo or atomoxetine).”, while Section 4.3 defines

CONFIDENTIAL

Project Document Version No. 2.0

Effective Date: 30 Jan 19

Project Document Effective Date: Date of last signature

Related to: [REDACTED]

Page 40 of 41

treatment compliance percentage via number of tablets, the treatment compliance used for analysis of TS14 is according to SAP Section 4.9.2 based of days of study drug intake, not the number of tablets, which is used to monitor study conduct.

Changes

Not applicable.

